j. Soot	1 	2  →	 
k. Creosote	1 	2  →	 
l. Inks, dyes, tanning solutions	1 	2  →	 
m. Dry cleaning agents	1 	2  →	 
n. Rubber and rubber products	1 	2  →	 
o. Vinyl chloride, plastics	1 	2  →	 
p. Acrylic and oil-based paints	1 	2  →	 
q. Varnish, lacquers, or glues	1 	2  →	 
r. Paraffin waxes	1 	2  →	 
s. Coal dust	1 	2  →	 
t. Metals (lead, nickel, zinc)	1 	2  →	 
u. Radioactive materials	1 	2  →	 
v. X-ray machines	1 	2  →	 

Information About Your Home

We are interested in chemicals that may have been used in places where you lived, including inside homes, on lawns/yards, or on family gardens. Do not include use of these chemicals if they were used as part of your job (such as farming activities, work at a nursery, or other workplace that uses these chemicals).

86. Have insecticides (chemicals that kill insects) ever been used around your home, lawn/yard, or family garden at any of the residences where you have lived?

1 No → **Go to question 89.**
2 Yes

87. If yes, approximately how many years (total) were these products used?

1 4 years or less
2 5 to 15 years
3 16 to 30 years
4 31 years or more

88. Did you personally handle any of these products?

1 No
2 Yes

89. Have fertilizers (not including pesticides) ever been used on lawns/yards at any of the residences where you have lived?

1 No → **Go to question 92.**
2 Yes

90. Approximately how many years (total) were these products used?

1 4 years or less
2 5 to 15 years
3 16 to 30 years
4 31 years or more

91. Did you personally handle any of these products?

1 No
2 Yes

92. Have herbicides (chemicals that kill weeds) ever been used around your home, lawn/yard, or family garden at any of the residences where you have lived?

1 No ————— **Go to question 95.**

2 Yes

93. If yes, approximately how many years (total) were these products used?

1 4 years or less

2 5 to 15 years

3 16 to 30 years

4 31 years or more

94. Did you personally handle any of these products?

1 No

2 Yes

95. Have pesticides or chemicals to control or prevent termites ever been used at any of the residences where you have lived?

1 No ————— **Go to question 98.**

2 Yes

96. If yes, approximately how many years (total) were these products used?

1 4 years or less

2 5 to 15 years

3 16 to 30 years

4 31 years or more

97. Did you personally handle any of these products?

1 No

2 Yes

98. Have you ever had cats as pets?

1 No → **Go to comments below.**
2 Yes

99. If yes, did a veterinarian ever tell you that any of your cats had feline leukemia or lymphoma?

1 No → **Go to comments below.**
2 Yes

100. If yes, how many of your cats had feline leukemia or lymphoma?

Cats

Comments:

Please provide any comments or additional information below.

ALESE Study Future Contact

*To maintain your confidentiality, this page will be stored
separately from your responses to the survey.*

A. How was the survey completed?

1 I filled it out myself

2 Someone helped me fill it out

3 Spouse

4 Child

5 Other, please specify: _____

B. What is your date of birth? / / Year
Month Day Year

C. Would you like to receive any updates or study results?

1 No

2 Yes

D. We would like to know if it would be okay to contact you in the future to see if you have learned anything more about your family health history and to record any changes. This would probably be about 3 to 5 years from now. Would this be okay?

1 No

2 Yes

Please turn to the next page.

Please record your name and address so that we may contact you in the future:

Name _____
Street _____
Address _____
City, State Zip _____
Phone (_____) _____ - _____

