and run by [name] at the University of Minnesota identified > 600 new cases of myeloid leukemia (including n=393 AML) and 682 controls. The PALM study employed a straightforward self-administered questionnaire, and preliminary analyses confirm the significant association between prior regular aspirin (RR 0.6 in women) and acetaminophen (RR 1.5) use and development of AML (*in press*, Ross JA, et al Cancer Epi Biom Prev, July 2011), and has also identified prior obesity at ages 35 & 50 years with an increased risk of adult AML¹³⁸ (RR ~ 2). Importantly, a significant association between both previous medical history¹³⁹ and family history and the development of AML has been identified from the PALM study, although that data is still being analyzed and has not yet been presented. The prevalence of common exposures among n=682 controls from the PALM study is included in the Table (below).

Table: Prevalence of common exposure from PALM study control population (*personal communication, [name], Univ. of Minnesota*)

Exposure	PALM Question #	Prevalence in Controls (n=682)
Benzene	85c	7%
Ever Smoked in lifetime	10	48%
Aspirin*	31a	27%
Rural/Farm – ever lived	67	**58%

* *more than occasionally*

***Rural/Farm is expected to be significantly lower in ECOG trial, as PALM study included only Minnesota residents*

While some of these factors are potentially modifiable, a critical question remains as to the impact of these common exposures on subsequent AML survival. Patients with t-AML have been shown to have an inferior outcome, although this is highly dependent on the specific cytogenetic abnormality¹³⁴. However, the impact of other potential etiologic factors (in particular prior exposures, lifestyle factors, and medical/family history) on survival after AML is not known. The PALM study was itself not designed to study subsequent leukemia clinical outcomes.

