A large multicenter cooperative group study affords a unique and highly attractive opportunity to prospectively study the impact of these established prior exposures/potential etiologic factors on AML survival in a controlled clinical setting. Indeed, E2906 is uniquely positioned to prospectively study their impact on AML survival for several reasons: it is a large prospective trial; it is focused on the largest group of patients with AML (age >60 years) and is broadly inclusive; the clinical endpoints are well-defined; genetic and molecular subtypes of AML will be extremely well-characterized; and it controls strictly for therapy. The questionnaire is designed to be self-administered in < 20 minutes

(unless significant farm exposures - 20-30 minutes), and will add minimal additional burden to site research personnel and patients during their initial 1-month hospitalization.

We therefore propose to formally study the impact of underlying exposures and lifestyle factors associated with AML development on subsequent clinical outcomes, and specifically on overall survival. Adapting the self-administered PALM tool for use in E2906 in collaboration with [name], Univ. of Minnesota (the "Acute Leukemia Epidemiology & Survival in ECOG" - "ALESE" questionnaire), we will offer patients the opportunity to participate in a prospective study which will evaluate the presence of these previously-identified exposures/potential etiologic factors among AML patients and study their impact on subsequent survival after therapy with curative intent. The use of the ALESE tool will allow an opportunity to normalize our case data from E2906 with the results of the PALM Minnesota population-based case-control study to determine important similarities and differences, in order to better understand the prevalence of individual exposures & lifestyle factors in the broader AML population receiving therapy with curative intent. In addition, the availability of this prospective clinical data on lifestyle, family/medical history & exposure will be an invaluable resource in the future for the correlation of specific exposures with well-characterized genetic & molecular subgroups of AML (as will be performed in E2906), allowing a planned future study of the molecular epidemiology of AML & clinical outcomes.

METHODS

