2.2 Secondary Objectives

2.2.1 To evaluate complete remission (CR) rates, duration of remission, and toxicity/treatment-related mortality of clofarabine in comparison with standard therapy (daunorubicin & cytarabine) in newly-diagnosed AML patients age \geq 60 years.

2.2.2 To evaluate the feasibility of consolidation with reduced-intensity conditioning and allogeneic hematopoietic stem cell transplantation from HLA-identical donors in patients who achieve a response to induction therapy, including the incidence of successful engraftment, acute and chronic graft-versus-host disease, transplant-related mortality, and its impact on overall survival in comparison to patients receiving chemotherapy.

2.2.3 To evaluate the duration of remission and disease-free survival of patients in complete remission following completion of consolidation therapy who are subsequently randomized to receive scheduled low-dose decitabine maintenance in comparison with observation.

2.2.4 To perform expression and methylation profiling on all patients receiving decitabine and to correlate their integrated epigenetic signatures with response to decitabine.

2.2.5 To examine the epigenetic profiles of remission marrow in patients randomized to observation vs. decitabine to determine whether epigenetic signature of apparently morphologically normal bone marrow is predictive of relapse or response to decitabine maintenance.

2.2.6 To explore the possible association of response to clofarabine with ABC-transporter P-glycoprotein (Pgp).

2.2.7 To assess the intensity of expression of CXCR4 on diagnostic leukemia cells and to correlate this parameter with other established prognostic factors

2.2.8 To assess the entire spectrum of somatic mutations and affected pathways at diagnosis of AML and elucidate the association between gene mutation and outcome.

2.2.9 To examine the impact of smoking, obesity, regular acetaminophen use, regular aspirin use, benzene exposure, living in a rural/farm environment and some other underlying exposures and lifestyle factors associated with AML development on OS.

Rev. 2/13

Rev. 2/12

Rev. 2/12

Rev. 2/13

Rev. 2/13

2.2.10 To investigate potential correlative results between array CGH findings and acute myeloid leukemia patient characteristics.

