9.6 AML Clinical Epidemiology

We assume that approximately 600 (82% of all 727 registered to Step 1) patients will complete the ALESE questionnaire. The proportions of obese patients and patients who had benzene exposure, ever smoked in their lifetime, took aspirin regularly, took acetaminophen regularly, ever lived in rural/farm environments, or had other exposures or lifestyle factors will be calculated separately, along with their 95% CIs. With 600 patients, the width of the 95% CI will be no wider than 0.08.

We will examine the impact of smoking, obesity, regular acetaminophen use, regular aspirin use, benzene exposure, and living in a rural/farm environment on OS. The impact of some other exposures or lifestyle factors on OS will also be explored. Assume 50% patients ever smoked in lifetime and assume for those patients a 10% long-term cure rate and 8-month median overall survival in the non-cured group. With treatment arms combined, the study will have approximately 80% power to detect a 22% reduction in the hazard rate in non-smoking patients, using a one-sided log rank test at the significance level of 0.025 and assuming 2 years of follow-up. The number of events needed is 502. Assume 20% patients had benzene exposure and assume those patients have a 10% long-term cure rate and 7.5 -month median overall survival in the non-cured group. With treatment arms combined, the study will have approximately 80% power to detect a 27% reduction in the hazard rate in non- benzene- exposure patients, using a one-sided log rank test at the significance level of 0.025 and assuming 2 years of follow-up. The number of events needed is 482. When data are available, a one-sided log-rank test stratified by induction treatment effect will be used to evaluate the impact of those exposures or lifestyle factors on OS. Moreover, the weighted analysis as described in Section [9.2](#) will also be used in order to reduce the potential bias from the maintenance therapy. Patients receiving alloSCT will be included in this analysis.

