- EDB, E-D-Bee, Bromofume, or other ethylene dibromide products (no longer on the market)

82. Are there any other pesticides you were exposed to?

1 No

2 Yes (If yes, please list them below and include reason for use.)

83. What has been your usual job during most of your adult life, that is, the job or type of job you have held the **longest**? (Please record your job title. For example: gasoline engine assembler, grinder operator, farmer, homemaker, sales manager, registered nurse, etc. If military – please include description of job duties and highest rank.)

Job Title: _____

Description: _____

84. For how many years did you work at this job?

Years

85. Have you ever been exposed to any of the following substances listed below, for at least 8 hours per week for 1 year or more, either on a job or working on a hobby? (Check no or yes beside each substance and if yes, write in approximately how many years you were exposed in the boxes provided.)

	No	Yes	Number of Years
a. Cutting oils, motor vehicle oils	1 	2  →	 
b. Asphalt, tar or pitch	1 	2  →	 
c. Benzene or other solvents	1 	2  →	 
d. Gasoline	1 	2  →	 
e. Pesticides	1 	2  →	 
f. Herbicides	1 	2  →	 

(Question 85 continued)

Have you ever been exposed to any of the following substances listed below, for at least 8 hours per week for 1 year or more, either on a job or working on a hobby? (Check no or yes beside each substance and if yes, write in approximately how many years you were exposed.)

	No	Yes	Number of Years
g. Fertilizers	1 	2  →	 
h. Arsenic	1 	2  →	 
i. Mineral oils	1 	2  →	 

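### The planned benzene analysis rests on a questionnaire item that combines benzene with other solvents, so its prevalence, survival test and power statement apply to the composite and not to benzene

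*Combined protocol and SAP*

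**What the plan says.** Objective 2.2.9 lists the exposures whose effect on overall survival will be examined, among them "regular aspirin use, benzene exposure, living in a rural/farm environment". Section 9.6 expects that "approximately 600 (82% of all 727 registered to Step 1) patients will complete the ALESE questionnaire". It will report the proportion with each exposure and a 95% confidence interval, and then test each exposure on overall survival. Benzene has its own power statement: "Assume 20% patients had benzene exposure", a 10% cure rate and a "7.5 -month median overall survival in the non-cured group" for those patients, and about 80% power for a 27% lower hazard in the unexposed, with a one-sided log-rank test at 0.025 and 482 events.

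Section 1.6.5 describes the questionnaire as made by "Adapting the self-administered PALM tool for use in E2906". Its table of control prevalences pairs the row labelled Benzene with question 85c. In Appendix V, item 85c reads "Benzene or other solvents". Question 85 asks about exposure "for at least 8 hours per week for 1 year or more, either on a job or working on a hobby", with one No/Yes answer and a number of years. No other ALESE item names benzene, and Section 9.6 gives no rule for deriving benzene exposure from the form.

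**The concern.** The objective names one chemical, while the item asks about that chemical or a wider class in one tick box. A patient exposed only to another solvent answers yes and enters the exposed group. Nothing in 85c separates the two kinds of patient, and the years field carries the same mixture.

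Two consequences need no assumption about effect sizes. The reported prevalence would be that of the composite under the name benzene. A survival difference could also come from benzene, from other solvents or from both, although the rationale in Section 1.6.5 concerns benzene. A third consequence is conditional: power for a benzene effect of the stated size may be below the stated 80%.

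**Working it through.** **Inputs.** From Section 9.6: 482 events, exposed share p = 0.20, hazard ratio 0.73 (unexposed to exposed), one-sided 0.025. Not in the documents, and therefore assumed: f, the share of 85c-positive patients who truly had benzene exposure, and c, the effect of other solvents as a fraction of benzene's log hazard ratio.

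**Reproducing the plan's figure.** The Schoenfeld approximation is power = Φ(|ln HR| × √(D·p·(1−p)) − 1.960).

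- √(482 × 0.20 × 0.80) = √77.12 = 8.782
- |ln 0.73| = 0.3147, and 0.3147 × 8.782 = 2.764
- Φ(2.764 − 1.960) = Φ(0.804) = 78.9%

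In the other direction, events for 80% power = (1.960 + 0.842)² / (0.16 × 0.3147²) = 496, against the stated 482. Expected events under the Section 9.6 cure model, with 600 patients, at least 24 months of follow-up and an assumed 48-month uniform accrual, come to 482.5. The plan's arithmetic holds for two groups whose hazard ratio is 0.73.

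**What that contrast is.** The only groups the form can supply are 85c-yes and 85c-no. The figure therefore belongs to a hazard ratio of 0.73 between those groups. It carries over to benzene if every yes is a benzene exposure, or if other solvents act on survival as strongly as benzene does.

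**If neither condition holds.** Keep 20% as the item-positive share and average the log hazard ratios within the exposed group. The multiplier on ln 0.73 is m = f + (1−f)·c, and power = Φ(2.764·m − 1.960).

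| f | c = 0 (others inert) | c = 0.5 | c = 1 |
|---|---|---|---|
| 1 | 79% | 79% | 79% |
| 0.75 | 54% (m = 0.75) | 68% (m = 0.875) | 79% |
| 0.50 | 28% (m = 0.50) | 54% (m = 0.75) | 79% |
| 0.25 | 10% (m = 0.25) | 41% (m = 0.625) | 79% |

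For f = 0.5 and c = 0: 0.5 × 2.764 − 1.960 = −0.578, and Φ(−0.578) = 28%. Averaging hazards instead of log hazards changes the c = 0 column little: at f = 0.5 it gives a hazard ratio of 1/(0.5/0.73 + 0.5) = 0.844 and power of 32%, and at f = 0.25 it gives 12%.

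**Attribution.** Reverse the roles: suppose benzene has no effect, other solvents have a hazard ratio of 0.73, and half of the positives had other solvents only. The averaged log hazard ratio is again 0.5 × ln 0.73, so the test labelled benzene would reject about 28% of the time, not 2.5%. The c = 1 column makes the same point from the other side: full power, but no way to say which exposure is responsible.

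**The case against.** The strongest reply has four parts.

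- **The analysis is not final.** Section 9.6 fixes no exposure rule, and Section 1.6.5 defers a detailed analysis plan to a grant application. The years field and the job title in Questions 83 and 84 could refine the exposure. This is true, but no such refinement is written down. Question 83 covers only the longest-held job, whereas Question 85 covers any job or hobby. As the plan stands, 85c is the only direct source.
- **The link to 85c is indirect.** Section 9.6 does not cite the item, the Section 1.6.5 table gives PALM question numbers, and PALM's own wording is not in the documents. However, ALESE is adapted from PALM, the numbering matches, and no other ALESE item names benzene.
- **The item is inherited, and comparability with PALM is a stated aim.** This stands as a reason to leave the item alone. It does not justify the narrower label.
- **It is one exposure within a secondary objective.** This also stands, and it limits the weight of the point.

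A reader might infer three stronger things, none of which the documents support. The first is that 85c captures any solvent. It does not: Question 85 requires at least 8 hours a week for a year or more, and gasoline, dry cleaning agents, paints, and varnish, lacquers or glues have their own lines. The second is that a benzene effect is necessarily diluted and that power is really 28% or 10%. Those figures need other solvents to be inert, on which the documents say nothing; a strong effect of other solvents would move the result the other way. The third is that the 80% is miscalculated. It reproduces.

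**Conclusion.** The exposure is mislabelled. The prevalence, the survival comparison and the power statement in Section 9.6 describe benzene or other solvents at the Question 85 threshold, and a result from 85c alone cannot be attributed to benzene. That conclusion rests on the wording of the item and on the absence of any other benzene item, not on the power figures.

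The loss of power is conditional. It arises only if some positive patients had no benzene exposure and other solvents affect survival less than benzene does. Its size depends on two unknowns; with half of the positives benzene-exposed, it runs from 28% power (others inert) to 54% (others at half the log hazard ratio). These scenarios also depart from Section 9.6, which takes 20% as the benzene-exposed share: at f = 0.5 the true share would be 10%. They illustrate sensitivity and do not correct the plan's figure. The primary survival comparison is unaffected.

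**What to change.** In Objective 2.2.9, Section 9.6 and the Section 1.6.5 table, rename the exposure *benzene or other solvents (item 85c, at least 8 h/week for 1 year or more)*. Because the table reports PALM data, check the new label there against PALM's own wording. In Section 9.6, attach the 20% exposed share and the 80% power to the composite, and add a sentence that no benzene-specific conclusion will be drawn from it.

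Leave the questionnaire item as it is. Splitting 85c may look attractive, but Step 1 accrual was suspended at 727 patients (Section 9.5), and Section 6.8 allows later completion only in survivors. A new form would reach few patients, selected for survival, and would leave two versions of the item. Keeping the item also preserves the comparison with PALM.

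The cost is a few words in three places and a less specific claim. No new patients or data are needed.
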